6.6.5 Expectedness

In a previous clinical trial where CSA concentrations ranged from 0.1% to 0.4% in the treatment of moderate-to-severe dry eye, AEs were uncommon and no significant AEs were reported (Stevenson, 2000).

In more recent studies by Sirion Therapeutics comparing CSA 0.1% to vehicle in treating moderate-to-severe dry eye, the AE's reported most frequently among both the CSA-treated and vehicle-treated subjects were as follows: eye irritation, conjunctival hyperaemia, ocular hyperaemia, dry eye, and foreign body sensation in eyes (Data on File, 2008).

Unexpected AEs are defined as any AE, the specificity or severity of which is not consistent with the current Investigator's Brochure.

6.6.6 Clinical Significance

The medical monitor, in consultation with the Investigator, will be responsible for determining whether an AE is clinically significant for the subject or the study overall.

6.6.7 Serious Adverse Events

6.6.7.1 Definition

An SAE is defined by federal regulation as any AE occurring at any dose that results in any of the following outcomes: death, life-threatening AE, hospitalization or prolongation of existing hospitalization, a persistent or significant disability/incapacity, or a congenital anomaly/birth defect.

Important medical events that may not result in death, be life-threatening, or require hospitalization may be considered an SAE when, based upon appropriate medical judgment, they may jeopardize the subject and may require medical or surgical intervention to prevent one of the outcomes listed in this definition. Examples of such medical events include allergic bronchospasm requiring intensive treatment in an emergency room or at home, blood dyscrasias, or convulsions that do not result in inpatient hospitalization, or the development of drug dependency or drug abuse.

6.6.7.2 Reporting Serious Adverse Events

To report an SAE, complete the online eCRF within 24 hours of the Investigator being notified of the event.

Specific medical questions can be addressed to the medical monitor.

[name], Medical Monitor
[contact], [name] (office)
[contact] (after hours)
[contact] (mobile)
[contact] (fax)
E-mail: [contact]

All follow-up information to SAEs should be provided to Sirion Therapeutics within 3 calendar days of receipt at the site.

The Investigator must notify the approving IRB of any SAEs regardless of cause within 24 hours. Sirion Therapeutics will be responsible for reporting SAEs to the FDA.

6.7 Concomitant Medication Documentation

Concomitant medications should be reviewed upon arrival at each study visit for any changes since the last visit. Changes and the reason for the change should be recorded on the Concomitant Medication form of the eCRF.

6.8 Removal of Subjects From the Trial or Study Drug

In the event that it is judged by the Investigator that the subject should be withdrawn from the trial and after discussion with the medical monitor, then the subject should be withdrawn and treated at the discretion of the Investigator. The last measured values on the efficacy measures will be carried forward from that point.

The Investigator may withdraw a subject from study treatment for any of the following reasons:

- The subject withdraws consent
- The Investigator believes that continuation in the trial is contrary to the subject's best interests
- A protocol violation occurs
- The subject is lost to follow-up
- A serious or intolerable AE occurs
- The sponsor or Investigator terminates the study

If the subject is withdrawn from study treatment prematurely, providing the subject has not withdrawn consent, all of the Day 90 measures (Section 6.2.5) should be performed as soon as possible following the final dose of study drug. If the subject is lost to follow-up, 2 documented attempts should be made to contact the subject to return for a final evaluation. If it is necessary for the subject to attend the clinical site for an unscheduled visit, the appropriate observations/evaluations will be performed and recorded on the applicable eCRF page.

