3.3 Study Duration and Dates

The duration of study treatment is 90 days, with the primary efficacy assessment at Day 90. Safety and efficacy evaluations will be conducted at Days 14 (± 3 days), 28 (± 3 days), 42 (± 3 days), 60 (± 3 days), and 90 (± 3 days).

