5.2 Treatments Administered

Subjects who meet inclusion criteria at baseline (Day 0) will be randomized to 1 of 3 treatment groups:

Treatment Group 1: Approximately 65 subjects will receive 1 drop of CSA 0.1% per eye 2 times per day (BID) for 90 days

Treatment Group 2: Approximately 65 subjects will receive 1 drop of CSA 0.2% per eye BID for 90 days

Treatment Group 3: Approximately 65 subjects will receive 1 drop of vehicle per eye BID for 90 days

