5.5.1 Unmasking During the Study Period

Should it be necessary to unmask a subject's treatment assignment in case of emergency, the Investigator should follow the procedure outlined below. The randomization code is to be obtained only if a medical emergency exists and knowledge of the medication being taken will influence the medical management of the subject. In the event of emergency or life-threatening condition, the Investigator may need to unmask the subject.

The following procedure should be followed:

1. The Investigator should contact Sirion Therapeutics immediately before unmasking a subject unless it is not possible to do so without risk to the subject. If the cannot contact the Medical Monitor and the situation is an emergency, the clinical trial material labeler should be contacted. The contact number can be found on the label of the clinical trial material as well as provided with the clinical trial material shipments.
2. The Investigator should document the adverse event (AE) or serious AE (SAE) and justification for unmasking in the eCRF. This information should be noted in the relevant AE or SAE eCRF form.
3. The subject may continue to participate in the study at the Investigator's discretion. If the subject is withdrawn from study treatment prematurely, all of the measures should be performed as soon as possible following the final dose of study drug providing the subject has not withdrawn consent and recorded on the appropriate eCRF.
4. The Investigator should contact Sirion Therapeutics within 24 hours with the randomization number, subject initials, details of the AE or SAE, any action taken, and whether the subject is continuing in the study.

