6.6.2 Timing

Any AE that begins on or after baseline (Day 0) following the initial dose of study medication until the end of the treatment period (Day 90) is to be recorded in the appropriate section of the eCRF. Subjects with an AE should be carefully followed to determine outcome until resolution or 30 days after the last study visit, whichever comes first.

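### Protocol 6.8 and 5.5.1 do not keep the scheduled Day 90 visit for consenting subjects who stop study drug, so the primary outcome need not be collected for them

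*Protocol*

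**What the plan says.** Section 3.2.1 defines both primary endpoints (lissamine green staining and stickiness frequency) as change from baseline at Day 90. Section 3.3 repeats the time point: "The duration of study treatment is 90 days, with the primary efficacy assessment at Day 90". Section 3.1 schedules visits at Days 14, 28, 42, 60 and 90, each ±3 days. Neither 3.1 nor 3.3 says whether the schedule still binds a subject who has stopped drug.

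Section 6.8 deals with removal from the trial and removal from study drug together:

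- After withdrawal from the trial: "The last measured values on the efficacy measures will be carried forward from that point".
- The list of reasons opens with "The Investigator may withdraw a subject from study treatment for any of the following reasons", but the list includes withdrawn consent, loss to follow-up and termination of the study.
- For a consenting subject withdrawn from treatment: "all of the Day 90 measures (Section 6.2.5) should be performed as soon as possible following the final dose of study drug".
- For a subject lost to follow-up: "2 documented attempts should be made to contact the subject to return for a final evaluation".

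Step 3 of 5.5.1 lets an unmasked subject stay in the study if the investigator so decides. If that subject is withdrawn from treatment and still consents, "all of the measures should be performed as soon as possible following the final dose of study drug".

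The only later follow-up that the available text clearly requires is of adverse event outcomes, "until resolution or 30 days after the last study visit, whichever comes first" (6.6.2, and likewise 6.6.1).

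**The concern.** The instruction in 6.8 brings the Day 90 assessments forward to just after the last dose and then stops. It does not say that the prompt exam replaces the Day 90 visit, but a site can easily read it that way. The exam carries the Day 90 name, nothing later is asked for except adverse event outcomes, and the section treats stopping drug and leaving the trial as nearly the same event. The carry-forward sentence is written for withdrawal from the trial. Because the two events are mixed, a site could also apply it to someone who has only stopped drug.

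What is at stake is the primary outcome in a randomized comparison. Subjects who stop drug may differ from those who continue, and may differ by arm. If the Day 90 visit is held, the analysis can use the value or set it aside, according to what it aims to estimate. If it is not held, that choice is gone.

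**Working it through.** **The text.** The protocol states no figure on this point, so there is none to reproduce. The check sets four questions against the sections.

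| Question | Where | Answer in the text |
|---|---|---|
| When is the primary outcome due? | 3.1, 3.2.1, 3.3 | Day 90 |
| What is done when a consenting subject stops drug? | 6.8; 5.5.1 step 3 | Exam as soon as possible after the last dose |
| Must that subject also attend on Day 90? | 6.8; 5.5.1; 3.1; 3.3 | Not stated |
| What must be followed later? | 6.6.1; 6.6.2 | Adverse event outcomes |

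For a subject who stops at Day 14, an exam at that point falls 90 − 14 = 76 days before the time point of the primary endpoint.

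**The size, for scale only.** Inputs from the protocol:

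- About 65 subjects per arm, who "will be randomized to 1 of 3 treatment groups" (5.2): 3 × 65 = 195.
- Five post-baseline visits (3.1): 195 × 5 = 975 planned visits.
- Lissamine green: three areas, each 0–4 (6.4.1.1), so 0–12 when summed. Stickiness frequency: 0–3 (6.4.2.1).

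Assumed, because the available text does not give them: an early-stop rate *d* of 5–20%, and a share *r* of 50–80% of those who stop who still consent and can be reached.

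| Quantity | Formula | Low | High |
|---|---|---|---|
| All early stops (ceiling on those recoverable at that rate) | 195 × *d* | 9.75 (about 10) | 39 |
| Recoverable Day 90 values | 195 × *d* × *r* | 9.75 × 0.5 = 4.9 (about 5) | 39 × 0.8 = 31.2 (about 31) |
| Per arm | 65 × *d* × *r* | 1.6 (about 2) | 10.4 (about 10) |
| Share of an arm | *d* × *r* | 0.025 | 0.16 |
| Share of planned visits | 195 × *d* × *r* / 975 | 0.5% | 3.2% |

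Suppose the early value stands in for Day 90. The arm mean then moves by *d* × *r* × *g*, where *g* is the average difference between the early value and the true Day 90 value in these subjects. That is 0.025–0.16 points for each point of *g*. The difference between arms moves only if *d* × *r* × *g* differs between arms. The protocol gives no basis for a value of *g*.

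**The case against.** The strongest objection is that the sections most likely to settle the matter were not available. The contents list 7.2.5 (Day 90 procedures), 9.1.1 (missing data) and Appendix 1 (schedule), and 3.1 refers the reader to Appendix 1. If one of them already requires the visit, the point shrinks to a missing cross-reference. This stands as a limit. It does not remove the problem in 6.8, which is the specific instruction a site will follow when a subject stops drug. The section's own pointer does not help either: it cites 6.2.5, which is not in the contents.

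Second, 6.8 does not state that the early exam replaces Day 90, and 3.1 and 3.3 exempt nobody. That is correct, and the finding is about silence where an instruction is needed. The final-evaluation wording concerns subjects lost to follow-up, so it is only weak support for the narrower reading. The carry-forward sentence likewise follows directly on withdrawal from the trial and is properly placed; only the mixed list of reasons makes its reach uncertain.

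Third, the magnitude rests on assumed rates and no bias is shown. This also stands. In addition, the synopsis and 4.1 describe the 195 as evaluable subjects, so the number randomized could be somewhat larger, although 5.2 uses about 65 per arm as the randomized groups.

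Fourth, an early exam with carry-forward is a coherent on-treatment approach for a pilot, and off-drug values may reflect other dry eye therapy. But collecting the Day 90 value does not commit the analysis to using it, whereas failing to collect it rules out every approach that needs it. Which visits are held is a protocol matter, not one for the analysis plan. Pilot or not, the synopsis sets two primary endpoints and a two-sided 0.05 level.

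**Conclusion.** The concern holds for the wording of 6.8 and 5.5.1. Neither section requires a consenting subject off study drug to attend the scheduled Day 90 visit, and a site that does exactly what 6.8 says can leave both primary endpoints unmeasured at their defined time.

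Under the assumed rates, this affects about 5–31 of 195 subjects (2–10 per arm). The effect on the treatment comparison cannot be sized or signed from the protocol. The change should be made, but no distortion of the result has been demonstrated. Confidence is medium, because Sections 7 and 9 and Appendix 1 could not be read.

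**What to change.** Amend 6.8 and step 3 of 5.5.1 as follows:

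1. Define stopping study drug and withdrawing from the trial as separate events, sort the listed reasons accordingly, and tie the carry-forward sentence to withdrawal from the trial only.
2. Keep the prompt exam, recorded as an early discontinuation visit.
3. Have consenting subjects off drug attend at least the scheduled Day 90 (±3 days) visit for lissamine green staining and symptom frequency. Record off-drug status, and enter any new dry eye therapy on the existing Concomitant Medication form (6.7).

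The decision to stop drug stays with the investigator. If 7.2 or Appendix 1 already requires the visit, a pointer from 6.8 and 5.5.1 is enough. In the same sentence of 6.8, correct the reference to Section 6.2.5 to 7.2.5.

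The cost is amendment wording and a Day 90 visit for about 5–31 subjects under the assumptions above, from visits the schedule already contains. The drawback is that some of the values will be off drug, and some will follow new dry eye therapy.

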6.9 Appropriateness of Measurements

All of the measurements used in this study are standard, recognized methods of assessing the safety and tolerability of ophthalmic products and are commonly employed in clinical trials in the area of ophthalmology.
